2 SYNOPSIS

Title	An observational case control study of the use of siltuximab (SYLVANT) in patients diagnosed with COVID-19 infection who have developed serious respiratory complications
Developmental Phase	This is an observational case control study.
Institution	Azienda Socio-Sanitaria Territoriale Papa Giovanni XXIII, Bergamo, Italy
Study Centers	1 study center
Background	This observational study will collect data from patients treated under this already approved compassionate use program. The compassionate use programme was for treatment with SYLVANT siltuximab 400mg in patients diagnosed with COVID-19 infection who have developed serious respiratory complications.
	This observational study will group the patients into two cohorts receiving siltuximab. Patients in Cohort A are treated in a non-ICU setting and patients in Cohort B are in an ICU setting.
	Each patient will have a matched case control receiving standard treatment without siltuximab.
Objectives and	Primary objective
Endpoints	Cohort A: reduction of the need of invasive ventilation or 30-day mortality
	Cohort B: reduction of mortality
	Secondary objectives
	Cohort A
	Reduction of the need of time of ventilatory support
	Improvement of the lung function
	Improvement of radiologic findings
	Cohort B
	Reduction of days of need of intubation
	Percentage of patients that undergo to tracheostomy
	Improvement of the lung function
	Improvement of radiologic findings
	Primary endpoint:
	Cohort A: Reduction of the rate of need of invasive ventilation or 30-day mortality
	Cohort B: Reduction of length of ICU staying or 30-day mortality
	Secondary endpoints:
	Cohort A
	Reduction of days of need of ventilatory support
	Improvement of P/F fraction (resolution of ARDS i.e. P/F>300, or increase from baseline value of at least 50% if P/F>100 or 100% if P/F<100, at day 3, 8 and 15)

Reduction of the duration of invasive ventilation or length of ICU

Improvement of radiologic imaging

Cohort B

Reduction of days of need of intubation

Percentage of patients that undergo tracheostomy

Improvement of P/F fraction (resolution of ARDS i.e. P/F>300, or increase from baseline value of at least 50% if P/F>100 or 100% if P/F<100, at day 3, 8 and 15)

Improvement of radiologic imaging

• Exploratory end points

Correlation of outcomes with IL-6 levels

Study Design

This is a single-center observational case control study in Italy that follows the use of treatment with siltuximab in patients with COVID-19 who have developed serious respiratory complications. Retrospective data collection will be carried out on those patients who have received the drug through the compassionate use program (this program is still ongoing, and enrolling patients).

Patients receiving siltuximab that will be included into this observational study will be divided into 2 cohorts, and per current estimation split in a 3:1 ratio: 75% will be in Cohort A as not treated in an ICU setting and are not on mechanical ventilation, while 25% will form Cohort B and consists of patients in an ICU setting who are receiving invasive ventilation.

Each patient will be matched to a consented case control patient receiving treatment other than siltuximab for their condition.

Match Criteria

Patients and controls will be matched according to the following criteria:

- Age (by decades)
- Sex (M/F)
- P/F fraction (<100, 100-150 or >150) at baseline
- Antiviral therapy

Procedures outlined in this protocol are based on the compassionate use program, where patients are managed as per clinicians' best judgement and best practice. No clinical procedures are required by this observational protocol. Data on the procedures already performed during the routine diagnosis and treatment of COVID-19 patients will be collected. The list of clinical and laboratory parameters is provided to direct data collection for this observational study (as available in the medical records).

During their hospitalization, patients will be monitored as per standard hospital practice or as per national (emergency) guidelines in accordance with extraordinary circumstances relating to the COVID-19 outbreak. After discharge, patients will be asked to provide (from their primary health care providers) relevant laboratory results for 30 days following start of COVID-19 treatment via ventilation (either mechanical or non-invasive).

Data Collected

Data collection for this study will be on the basis of existing medical records i.e. from standard practice tests at the hospital. The following data will be collected /recorded (if available):

• Laboratory-confirmed COVID-19 test and date of diagnosis;

- Other medical history;
- Concomitant medications.

The following data will be recorded from the time of first ventilation for 30 days (if available):

- General information:
 - o Hospital admission date;
 - ICU admission (if applicable);
 - Mobility;
 - o Respiratory parameters;
 - o Use of inotropic medication;
 - o RR/MAP;
 - Diagnostic interventions (X-ray of thorax, computerized tomography [CT] scans);
 - o Symptoms (fever, rash, abnormal cardiac function);
 - o Mechanical ventilation;
 - o Extracorporeal membrane oxygenation (ECMO).
- Infectious Disease Parameters:
 - Inflammatory markers;
 - Peripheral edema;
 - O Cytokine panel (full work-up pre- and post-treatment [serum]);
 - o Pre-treatment C-reactive protein (CRP) levels;
 - o Post-treatment CRP levels/24 h
 - Cardiac parameters/oxygen saturation;
- General Disease Parameters:
 - APACHE II score;
 - Performance status (Eastern Cooperative Oncology Group [ECOG]/Karnofsky);
 - o Laboratory assessments;
 - Virus titer;
 - o IL-6 status: pre-treatment serum IL-6 levels (ELISA or similar approach, e.g. multiplex cytokine array);
 - Extended blood panel (hemoglobin/hematocrit [Hb/Ht]), thrombocytes (including peripheral blood mononuclear cell [PMBC]);
 - Coagulation status;
 - o History of Human Immunodeficiency virus (HIV), Human herpes virus (HHV-8), hepatitis and tuberculosis infection.

	-
Inclusion Criteria	Patients must meet the following criteria to be eligible to participate in the study:
	1. Clinical and radiological diagnosis of pulmonary infection by COVID-19
	2. Positive microbiological evidence of SARS-CoV-2 infection
	3. Diagnosis of acute respiratory distress syndrome clinical panel in accordance with Berlin 2012 criteria
	4. For Cohort A only: subjects are eligible if they are enrolled and treated within 48 hours from the beginning of NIV or CPAP
	5. For Cohort B only: subjects are eligible if they are enrolled and treated within 48 hours from the beginning of invasive ventilation
Exclusion Criteria	Patients who meet the following criteria may NOT participate in the study.
	1. Active infection of bacterial or viral (non COVID-19) origin
Number of Patients	Up to 50 patients: 50% receiving treatment (Cohort A and Cohort B) and 50% matched case controls.
Countries/Number of Sites	1 site in Italy
Statistical Methods	All data will be summarized using descriptive statistical analyses as appropriate.
	All data will be presented in by-subject data listings.

PROTOCOL APPROVED BY PRINCIPAL INVESTIGATOR

Name / Title: [name] PhD

Address: [name]
Contact Info: UOC Ematologia

4 LIST OF ABBREVIATIONS AND DEFINITION OF TERMS

Abbreviation	Term
AE	Adverse Event
ARDS	Acute respiratory distress syndrome
CRF	Case Report Form
CRP	C-reactive protein
CT	Computerized tomography
ECOG	Eastern Cooperative Oncology Group
EDC	Electronic Data Capture
ECMO	Extracorporeal membrane oxygenation
GCP	Good Clinical Practice
h	Hour
Hb	Hemoglobin
HHV-8	Human Herpes Virus-8
HIV	Human Immunodeficiency Virus
Ht	Hematocrit
ICH	International Council for Harmonization
IEC	Independent Ethics Committee
IL-6	Interleukin-6
ISO	International Organization for Standardization
MAP	Mean Arterial Pressure
N	Number
NIS	Non-Interventional Study
PBMC	Peripheral blood mononuclear cell
P/F	Peak flow
RA	Regulatory Authority
RR	Respiratory Rate
SAE	Serious Adverse Event
SD	Standard Deviation

5 INTRODUCTION

Coronaviruses (CoV) are a large family of viruses that cause illness ranging from the common cold to more severe diseases such as Middle East Respiratory Syndrome (MERS-CoV) and Severe Acute Respiratory Syndrome (SARS-CoV). A novel coronavirus (nCoV) is a new strain that has not been previously identified in humans (WHO).

One of the most serious potential symptoms that can occur with a coronavirus is the so-called 'cytokine storm' – when the immune system becomes over-stimulated and begins to attack a patient's own body. It has already been recognized that potential symptomatic treatment of critically ill COVID-19 infected patients should be directed towards reducing excessive immune response (A. Zumla, DS Hui et al.)

Medics already have considerable experience managing cytokine storms and excessive immune reaction with IL-6 blockers like tocilizumab. Roche has secured approval from China for its anti-inflammation drug Actemra (tocilizumab) to treat patients developing severe complications from coronavirus (COVID-19). In its latest treatment guidelines published online, the commission said that the biologic drug Actemra can now be used to treat coronavirus patients with severe lung damage and high IL-6 levels (Pharmaceutical-technology.com).

SYLVANT® (siltuximab) is a monoclonal antibody that prevents IL-6 from binding to IL-6 receptors and therefore causes blockade of IL-6 (EUSA Pharma UK).

In the Compassionate Use Program, critically ill COVID-19 patients (with a confirmed diagnosis) with severe acute respiratory distress will be treated with a single intravenous infusion of siltuximab (SYLVANT), Blocking of the excessive IL-6 could diminish the excessive immune response and consequently reduce its toxic effect on lungs. Early control of excessive immune response in acute respiratory distress syndrome may reduce mortality and might also ensure faster recovery with milder consequences.

This observational case control study will collect and analyze the data from patients who were treated under the compassionate use program (still ongoing). This study will assess the treatment effects of siltuximab in diagnosed COVID-19 patients with serious respiratory complications and could provide valuable insight into the development of treatments for patients with COVID-19.

5.1 Study Rationale

There is an emergency situation regarding treating patients with COVID-19 and especially those with lung complications and/or acute respiratory distress syndrome (ARDS), which is the main cause of morbidity and mortality in these patients. Siltuximab (SYLVANT) 400 mg is an approved product and dosage for idiopathic Multicentric Castleman Disease (iMCD): it is not indicated for the treatment of COVID-19 infection. However, due to observed clinical (lung dysfunction) and laboratory (high IL-6) presentation in COVID-19 patients, siltuximab (an IL-6 blocker) may potentially benefit patients who developed respiratory complication.

As siltuximab is being used for the first time in this indication, there is a requirement to collect and analyze efficacy and safety data from both the standard of care and siltuximab

treated patients in order to assess risk/benefit as well as the dosing regimen of siltuximab in this patient population. As this is an observational case control study, only available data will be collected and analyzed.

6 STUDY OBJECTIVES

The is a case control study to observe treatment and collect data on two cohorts of patients treated with siltuximab and a corresponding case control group of patients who have developed severe respiratory complications with COVID-19 infection.

Primary objective

Cohort A: reduction of the need of invasive ventilation or 30-day mortality

Cohort B: reduction of mortality

Secondary objectives

Cohort A

Reduction of the need of time of ventilatory support

Improvement of the lung function

Improvement of radiologic findings

Cohort B

Reduction of days of need of intubation

Percentage of patients that undergo to tracheostomy

Improvement of the lung function

Improvement of radiologic findings

Primary endpoint:

Cohort A: Reduction of the rate of need of invasive ventilation or 30-day mortality

Cohort B: Reduction of length of ICU staying or 30-day mortality

Secondary endpoints:

Cohort A

Reduction of days of need of ventilatory support

Improvement of P/F fraction (resolution of ARDS i.e. P/F>300, or increase from baseline value of at least 50% if P/F>100 or 100% if P/F<100, at day 3, 8 and 15)

Reduction of the duration of invasive ventilation or length of ICU

Improvement of radiologic imaging

Cohort B

Reduction of days of need of intubation

Percentage of patients that undergo to tracheostomy

Improvement of P/F fraction (resolution of ARDS i.e. P/F>300, or increase from baseline value of at least 50% if P/F >100 or 100% if P/F<100, at day 3, 8 and 15)

Improvement of radiologic imaging

Exploratory end points

Correlation of outcomes with IL-6 levels

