8 OBSERVATIONAL PLAN

8.1 Overall Study Design and Plan – Description

This is a single-center, observational case control study in Italy that follows the use of treatment siltuximab in patients diagnosed with COVID-19 infection who have developed serious respiratory complications. Retrospective data collection will be carried out on patients who have received the drug through the compassionate use program. (this program is still ongoing, and enrolling patients).

Patients receiving siltuximab will be included into this observational study and will be divided into 2 cohorts, split in an approximate 3:1 ratio: 75% will be in Cohort A and are not in an ICU setting and are not on mechanical ventilation, while 25% will form Cohort B and consists of patients in an ICU setting who are receiving invasive ventilation.

[figure not shown]
Each patient will be matched to a consented case control receiving treatment other than siltuximab for their condition.

Match Criteria

Patients receiving siltuximab and controls will be matched according to the following criteria:

- Age (by decades)
- Sex (M/F)
- P/F fraction (<100, 100-150 or >150) at baseline
- Antiviral therapy

Figure 1: Study Design

Procedures outlined in this protocol are based on the compassionate use program, where patients are managed as per clinicians' best judgement and best practice. No procedures are required by this observational protocol. Data on the procedures already performed during the routine diagnosis and treatment of COVID-19 patients will be collected. The list of clinical and laboratory parameters is provided to direct data collection for this observational study (as available in the medical records).

During their hospitalization, patients will be monitored as per standard hospital practice or as per national (emergency) guidelines in accordance with extraordinary circumstances relating to the COVID-19 outbreak. After discharge, patients will be asked to provide (from their primary health care providers) relevant laboratory results for 30 days following start of COVID-19 treatment via ventilation (either mechanical or non-invasive).

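### The Cohort B primary endpoint adds ICU length of stay to a mortality-only objective through an undefined “or”, so the primary result is not fixed and its two parts can conflict

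*Protocol*

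**What the plan says.** Protocol section 6 gives the primary objective as "Cohort B: reduction of mortality", with no time point. The primary endpoint for the same cohort is "Cohort B: Reduction of length of ICU staying or 30-day mortality". The synopsis (section 2) carries the same pair, so this is not an isolated slip. No Cohort B objective, primary or secondary, mentions ICU stay.

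Cohort A is built differently. Its objective is "Cohort A: reduction of the need of invasive ventilation or 30-day mortality" and its endpoint is "Cohort A: Reduction of the rate of need of invasive ventilation or 30-day mortality". Both name the same two components, and both components are events.

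Section 8.1 describes the cohort: "25% will form Cohort B and consists of patients in an ICU setting who are receiving invasive ventilation". Section 10.1.1 limits most data to the 30 days after first ventilation. Section 11.2.3 plans descriptive and exploratory analysis of the endpoints and rules out statistical comparisons between treated patients and matched controls.

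**The concern.** There are two faults in the text itself.

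- **Objective and endpoint are not aligned.** Mortality is in both, but the endpoint adds a component that the objective lacks, and a 30-day horizon that the objective also lacks.
- **The endpoint has no defined value for a patient.** Length of stay is a number of days and death is a yes/no event. The protocol does not say whether *or* means a composite, two alternatives or two co-primary endpoints. On a plain reading, a favourable difference in either part could be presented as the primary finding.

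The second fault matters more because the parts are not independent. Every Cohort B patient starts in the ICU, and death ends the stay. A group with more deaths can therefore show a shorter raw stay.

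The setting makes this choice easy to exploit, even unintentionally. Data collection is retrospective (section 8.1), efficacy signals may be looked for during the study (section 11), and ad hoc results may be released (section 11.2.5). The part to be emphasised could thus be chosen after outcomes are known.

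**Working it through.** The protocol states no effect size, significance level, power or calculated sample size, so there is no figure to reproduce. The check compares the texts above and adds arithmetic on assumed stays.

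**Cohort B size (from the protocol).** Up to 50 patients, half of them treated (section 2), and 25% of the treated in Cohort B (section 8.1): 50 × 0.50 × 0.25 = 6.25. That is about 6 treated patients and 6 controls. One death moves a group's mortality by 1/6, about 17 percentage points.

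**Assumptions (the protocol gives none of these).**
- Survivors' ICU stay S is the same in both groups: 15, 20 or 25 days.
- Deaths occur in the ICU on day D = 5, 8 or 12.
- Mortality m is 20 points higher on siltuximab: 50% against 30%, or 60% against 40%.
- ICU entry and first ventilation fall on the same day.

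**Formulas.**
- Raw mean stay = (1 − m) × S + m × D. Treated minus control = −0.20 × (S − D).
- Mean ICU-free days to day 30, death = 0: (1 − m) × (30 − S). Treated minus control = −0.20 × (30 − S).

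The differences depend only on the 20-point gap, so both mortality pairs give the same results. Selected combinations, including the extremes:

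| S | D | Raw mean stay, treated − control | ICU-free days, treated − control |
|---|---|---|---|
| 15 | 12 | −0.6 | −3.0 |
| 15 | 5 | −2.0 | −3.0 |
| 20 | 8 | −2.4 | −2.0 |
| 25 | 12 | −2.6 | −1.0 |
| 25 | 5 | −4.0 | −1.0 |

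Over all nine combinations of S and D, raw stay is 0.6 to 4.0 days shorter on treatment, which looks favourable. ICU-free days are 1.0 to 3.0 fewer, which is unfavourable. Setting each death to a 30-day stay also makes treatment 1.0 to 3.0 days worse.

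**At the actual scale (6 per group, S = 20, D = 8).**
- Control, 2 deaths: (4 × 20 + 2 × 8)/6 = 16.0 days.
- Siltuximab, 4 deaths: (2 × 20 + 4 × 8)/6 = 12.0 days.
- ICU-free days: (4 × 10)/6 = 6.7 against (2 × 10)/6 = 3.3.

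Twice the deaths appears as a stay 4 days shorter. The mortality gap here is 2/6, about 33 points, so this example lies outside the 20-point range above.

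**Timing of death alone.** With 50% mortality and S = 20, moving deaths from day 15 to day 3 changes mean stay from 0.5 × 20 + 0.5 × 15 = 17.5 days to 0.5 × 20 + 0.5 × 3 = 11.5 days, with no change in mortality.

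**The case against.** The strongest case on the other side has four parts.

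- **A SAP could settle it.** Only the protocol is at hand, and how a death enters a duration is a derivation rule that a SAP commonly sets. That part stands. But which quantity is primary, and whether it matches the objective, are matters for the protocol. A SAP should not have to choose between the protocol's own statements.
- **There is no success rule.** Section 11.1 has no sample size estimation, section 11.2.3 excludes statistical comparisons of the endpoints, and section 8.2 frames the study as hypothesis-generating. Section 11.2 mentions exploratory tests and confidence intervals but sets no decision criterion. By-subject listings would make each death visible among about 6 patients per group. This limits the consequence to selective emphasis. It does not remove it, because section 8.2 justifies the controls as a means of comparing the groups directly and section 11 plans a descriptive comparison on the endpoints.
- **Mortality is in both statements.** This is correct: the endpoint extends the objective and does not reverse it.
- **Changing a primary endpoint after data have been seen can itself be data-driven.** This is fair, and the amendment has to address it.

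Three stronger readings are tempting and are not supported.

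- A reader might infer that the protocol counts early death as a benefit. It nowhere says so, and the mortality part scores the same death as harm. Early death looks favourable only on the stay component, and only if stay is summarised without a rule for deaths.
- A reader might infer that a harmful treatment could meet the primary endpoint. No criterion exists to be met.
- A reader might take "only available data will be collected and analyzed" (section 5.1) to drop the dead from the P/F response at days 3, 8 and 15. In context it describes reliance on existing records, and section 9.1.1 expressly provides for data from deceased patients. P/F improvement is a threshold response that a dead patient does not reach. Only the denominator is unstated, and that can be left to a SAP.

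**Conclusion.** The point holds as a defect in the definition of the Cohort B primary endpoint. It adds ICU stay, which no Cohort B objective contains, and joins a duration to a binary event without saying how. There is no single outcome per patient, and either part could be presented as the primary result.

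The parts can point in opposite directions. With mortality 20 points higher on treatment, raw mean stay looks 0.6 to 4.0 days better while ICU-free days are 1.0 to 3.0 days worse. These figures illustrate direction and order of size only. They rest on assumed stays, an assumed day of death, equal stay among survivors and an assumed mortality gap, none of which the protocol supplies.

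The practical weight is limited by the descriptive analysis and the small cohort. The correction is still worth making, because it decides what the primary result is and costs little.

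**What to change.** **Primary endpoint.** In sections 2 and 6, make 30-day all-cause mortality the single Cohort B primary endpoint and write the same 30-day horizon into the objective. The objective now says neither 30-day nor all-cause, so both terms are additions.

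**ICU stay.** Move it to a secondary endpoint: days alive and out of ICU to day 30, counted from first ventilation (the start of the data window in section 10.1.1), with 0 for patients who die. List raw stay by survival status. The day-30 limit also settles stays that run past the data window. Treating death as a competing event would be a workable alternative.

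**Other durations (optional).** The same death-aware summary suits "Reduction of days of need of intubation" and days of ventilatory support, and also the Cohort A endpoint "Reduction of the duration of invasive ventilation or length of ICU". These rules can sit in a SAP.

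**Cost.** The change is to wording and derived variables, with no extra patients or procedures. Section 13.3 requires ethics committee agreement to protocol changes. The amendment should state whether outcomes had already been reviewed when it was written. Mortality alone is also a coarse primary result at about 6 patients per group, in steps of about 17 points. Free-days are less familiar than raw stay, which the listing by survival status keeps available.

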11.1 Sample Size Determination

No statistical sample size estimation was performed. For this study patients from one single center in Italy will be enrolled as follows:

- All patients treated with siltuximab diagnosed with COVID-19 infection who have developed serious respiratory complications, and
- An equal number of case control patients that consented to their data collection.

It is estimated that in total up to 50 patients will be enrolled.

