11.2.3 Analysis of Endpoint Data

Data on the endpoints specific for the study cohort considered will also be analyzed by descriptive and exploratory statistical methods. Due to the small sample size statistical comparisons between the siltuximab treatment group and the matched control group will not be performed.

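### Cohort B's primary objective is mortality, but its primary endpoint adds ICU stay through an undefined *or*, so a shorter stay could be presented as the primary finding when mortality is no better

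*Protocol*

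**What the plan says.** Protocol section 6 and the Synopsis use the same wording for the primary objectives and endpoints.

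- Cohort B primary objective: "Cohort B: reduction of mortality".
- Cohort B primary endpoint: "Cohort B: Reduction of length of ICU staying or 30-day mortality".
- Cohort A primary objective: "Cohort A: reduction of the need of invasive ventilation or 30-day mortality".
- Cohort A primary endpoint: "Cohort A: Reduction of the rate of need of invasive ventilation or 30-day mortality".

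On size, the Synopsis gives "Up to 50 patients: 50% receiving treatment (Cohort A and Cohort B) and 50% matched case controls", and section 8.1 says that "25% will form Cohort B and consists of patients in an ICU setting who are receiving invasive ventilation". Section 11.1 adds: "No statistical sample size estimation was performed".

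On analysis, section 11 foresees a descriptive comparison of the siltuximab and control groups on the endpoints within each cohort. Section 11.2 describes the approach as exploratory. Section 11.2.3 states: "Due to the small sample size statistical comparisons between the siltuximab treatment group and the matched control group will not be performed". Section 11 also permits looks at the data during the study, and section 11.2.5 permits ad hoc analyses to be released at the physician's discretion.

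**The concern.** An endpoint should measure what its objective asks. In Cohort B the objective asks only about death, without saying by when. The endpoint brings in ICU stay, which appears in no Cohort B objective, primary or secondary. Cohort A shows that the authors could align the two: its objective and endpoint name the same two components.

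The joining word adds to the problem. In Cohort A, *or* links two yes/no events, and the natural reading is that a patient with either event counts. In Cohort B it links a number of days to a yes/no event, and the Protocol does not say how they are to be combined. One open reading is that either component may serve as the primary result.

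The two components can also disagree, because death ends an ICU stay. Data collection is retrospective, interim looks are allowed and results may be released ad hoc. Someone could therefore see both components before deciding which one to present as primary. The study is meant to inform the risk/benefit assessment of siltuximab (sections 5.1 and 8.2), so a favourable headline on ICU days beside an unfavourable death count would mislead.

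**Working it through.** The Protocol gives no power, effect size or expected rate, so there is no planned figure to reproduce. All mortality rates and ICU durations below are assumptions.

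**1. Objective against endpoint**

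| Cohort | Components in the objective | Components in the endpoint | Match |
|---|---|---|---|
| A | invasive ventilation; death by day 30 | invasive ventilation; death by day 30 | yes |
| B | death, no horizon | ICU stay; death by day 30 | no |

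The mismatch appears in both the Synopsis and section 6, so it is not a slip in one place.

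**2. Size of Cohort B**

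50 patients × 0.5 treated × 0.25 in Cohort B = 6.25, so about 6 siltuximab patients and 6 controls.

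**3. Effect of mortality alone on mean ICU stay**

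Let q be mortality, S the mean ICU days of survivors and D the mean ICU days of those who die, with deaths counted at their observed stay. Then

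mean stay = (1 − q)·S + q·D,

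and raising mortality from q1 to q2 changes it by −(q2 − q1)·(S − D). With q1 = 30% and q2 = 50%:

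| S | D | Mean at 30% | Mean at 50% | Change |
|---|---|---|---|---|
| 20 | 8 | 0.7×20 + 0.3×8 = 16.4 | 0.5×20 + 0.5×8 = 14.0 | −2.4 d |
| 20 | 12 | 17.6 | 16.0 | −1.6 d |
| 15 | 8 | 12.9 | 11.5 | −1.4 d |
| 15 | 12 | 14.1 | 13.5 | −0.6 d |

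The sign depends on D < S. If those who die stay as long as survivors or longer, extra deaths do not shorten the mean.

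**4. How often the components disagree with 6 per group**

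A simulation of 200,000 runs per setting used two independent groups of 6 (matching ignored). ICU stays were gamma with shape 4, mean 20 days in survivors and 10 days in deaths, capped at 30 days. Control mortality was 30%, 40% or 50%.

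| Result for the treated group | No true effect | True mortality 20 points higher |
|---|---|---|
| Fewer deaths | 38–39% | 15–16% |
| Fewer deaths or shorter mean stay | 77–79% | 76–77% |
| Shorter mean stay, deaths equal or higher | 39–40% | 61–62% |

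Under these assumptions, looking better on at least one component is about as common when treatment is harmful as when it does nothing. Mortality alone does separate the two situations.

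**5. The replacement secondary measure**

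For days alive and out of ICU to day 30 with death = 0, and ICU stay running from day 0, the mean is (1 − q)·(30 − S). With S = 20 it falls from 0.7×10 = 7.0 to 0.5×10 = 5.0 days when mortality rises from 30% to 50%. With S = 15 it falls from 10.5 to 7.5 days. Extra deaths now count against treatment whatever D is.

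**The case against.** The strongest reply is that this is a small, hypothesis-generating study with no treatment assignment. It has no alpha, no decision rule and no planned statistical comparison of the endpoints between groups. All data go into by-subject listings, and with about 6 pairs a full report would show deaths and ICU days together. A statistical analysis plan, not shown, may define how deaths enter the ICU measure. The contradiction could also be removed by widening the objective or defining a composite.

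Much of this stands, and it limits what may be claimed. A reader might infer any of the following, and the Protocol does not support them:

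- *The primary endpoint can be formally met by ICU stay alone, or type I error is inflated.* Sections 11.2 and 11.2.3 set no success criterion, so there is nothing to meet.
- *A duration and a death cannot form one composite.* They can; days alive and out of ICU is one. The defect is that the Protocol does not say how they combine.
- *ICU days before siltuximab are counted.* The start of the ICU stay is nowhere defined.
- *ICU stay could be halved while mortality doubles.* This can be constructed: 4 of 6 treated patients dying on day 5 against 2 of 6 controls dying on day 20, with every survivor staying 20 days, gives (4×5 + 2×20)/6 = 10 against (2×20 + 4×20)/6 = 20 days. The result leans on the assumed death times. If control deaths also fell on day 5, the control mean would be (2×5 + 4×20)/6 = 15 days.

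The reply does not remove the mismatch itself. An analysis plan can define a calculation, but the Protocol's objective and endpoint would still differ. The listings do not protect against an ad hoc release that leads with one component.

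**Conclusion.** The concern holds as an inconsistency that should be fixed. Cohort B's objective and primary endpoint differ in both places where they are stated, and the meaning of *or* is left open. The consequence is a descriptive primary result that could favour treatment on ICU days while mortality is unchanged or higher.

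The mismatch and the undefined *or* need no assumption. The shortening of mean stay by excess deaths needs two: deaths are counted at their observed ICU days, and they occur sooner than survivors' discharge. For a rise in mortality from 30% to 50%, the shift is then 0.6 to 2.4 days over the assumed stays of 15–20 days in survivors and 8–12 days in deaths. It is modest, and it runs in the misleading direction. Given the exploratory purpose and about 6 patients per group, this does not invalidate the study.

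**What to change.** In the Synopsis and section 6:

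1. Make 30-day all-cause mortality the Cohort B primary endpoint, and add the 30-day horizon to the Cohort B primary objective. This follows the objective that the Protocol already states.
2. Set day 0 at the start of invasive ventilation, the anchor of Cohort B's 48-hour entry criterion. The 30-day recording window in section 10.1.1 runs from first ventilation. For a patient who had non-invasive support first, state that recording covers 30 days from day 0.
3. Move ICU stay to the Cohort B secondary endpoints as days alive and out of ICU to day 30, with death by day 30 scored 0, always reported beside mortality.
4. Make sure the CRF captures dates of ICU discharge and death from the records. The data lists in the Synopsis and sections 10.1.1 and 10.1.8 name ICU admission but neither of these dates.

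The cost is a wording change, which section 13.3 makes subject to ethics committee approval, and two dates to be taken from existing records. The scientific price is that a shorter ICU stay alone can no longer be the Cohort B primary result.
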